8.1 Software

All analyses are performed using IBM SPSS Statistics for Windows, Version 23.0 (IBM Corp., Armonk, NY, USA). The Johnson–Neyman procedure (when triggered) is implemented using the PROCESS macro Version 4.2 (Model 1; Hayes, 2022).

8.2 Significance Level and Confidence Intervals

All hypothesis tests are two-sided with a nominal significance level of $\alpha = 0.05$. Confidence intervals are reported at the 95% level.

8.3 Reporting Conventions

- Continuous variables: mean (SD) for normally distributed data; median (IQR) for non-normal data.
- Categorical variables: frequency (%).
- Effect sizes: partial eta squared (η^2 ; small = 0.01, medium = 0.06, large = 0.14) for ANCOVA models; ΔR^2 for moderation models.
- P-values reported to three decimal places (values < 0.001 reported as "< .001").

9. Statistical Methods

9.1 Participant Disposition and Baseline Characteristics

Participant flow is summarized using a CONSORT 2025 flow diagram. Baseline demographic and clinical characteristics are summarized descriptively by group. Between-group comparability is assessed using independent-samples t-tests for continuous variables and chi-square (or Fisher's exact, as appropriate) tests for categorical variables, presented descriptively without inferential interpretation as the basis for primary inference.

9.2 Distributional Assumptions

Normality of continuous variables is assessed using the Shapiro–Wilk test together with visual inspection of histograms and Q–Q plots. Because raw RMSSD values are expected to be right-skewed, a natural log transformation is applied. Homogeneity of variance is assessed using Levene's test.

9.3 Primary Analysis (Conditional on Homogeneity-of-Slopes Test)

The primary analysis examines intraoperative lnRMSSD using a regression model that includes group, baseline lnRMSSD, the Group \times Baseline lnRMSSD interaction term, age, and sex. The homogeneity of regression slopes assumption is evaluated by the significance of the Group \times Baseline lnRMSSD interaction term. The analysis path is conditional on this test:

Path A — Interaction not significant ($p \geq .05$)

If the homogeneity-of-slopes assumption holds, the interaction term is removed and a standard ANCOVA is fitted:

$$\ln\text{RMSSD_T2} = \beta_0 + \beta_1 \times \text{Group} + \beta_2 \times \ln\text{RMSSD_T1} + \beta_3 \times \text{Age} + \beta_4 \times \text{Sex} + \epsilon$$

Results are reported as adjusted means (SE) per group, the adjusted between-group mean difference (IG – CG) with 95% CI, the F-statistic with degrees of freedom, p-value, and partial eta squared (η^2).

Path B — Interaction significant ($p < .05$)

If the homogeneity-of-slopes assumption is violated, the conditional treatment effect across the range of baseline lnRMSSD values is examined using the Johnson–Neyman (J–N) procedure (Hayes, 2022; Ji, 2016) — the standard methodological response to violation of the homogeneity-of-slopes assumption when the moderating variable is continuous. The full moderation model is retained:

$$\text{lnRMSSD_T2} = \beta_0 + \beta_1 \times \text{Group} + \beta_2 \times \text{lnRMSSD_T1} + \beta_3 \times (\text{Group} \times \text{lnRMSSD_T1}) + \beta_4 \times \text{Age} + \beta_5 \times \text{Sex} + \epsilon$$

Results are reported as: (i) the overall model F-statistic and R^2 ; (ii) the Group \times Baseline lnRMSSD interaction F-statistic, p-value, and ΔR^2 ; (iii) the J–N region(s) of significance; and (iv) the proportion of the analyzed sample that falls within each region. Conditional simple effects are plotted across the observed range of baseline lnRMSSD.

The primary analysis is performed in the FAS (ITT).

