9.4 Secondary Analyses

Postoperative STAI-State and postoperative VAS are each analyzed using ANCOVA with the following model:

$$\text{Outcome_T3} = \beta_0 + \beta_1 \times \text{Group} + \beta_2 \times \text{Baseline} + \beta_3 \times \text{Age} + \beta_4 \times \text{Sex} + \epsilon$$

Where Baseline = STAI-State_T1 or VAS_T1, respectively. The homogeneity-of-slopes assumption is evaluated prior to each ANCOVA by testing the Group \times Baseline interaction. If violated for a secondary endpoint, the J–N procedure is applied analogously to the primary analysis. ANCOVA is selected for its robustness to deviations from normality given the sample size ($n > 30$ per group); where Shapiro–Wilk indicates substantial departure from normality, a non-parametric supportive analysis (Mann–Whitney U on change scores or rank-based ANCOVA) is reported.

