9.6 Subgroup Analyses (Exploratory)

Exploratory subgroup analyses examine consistency across: sex (male/female), age (< 60 vs. ≥ 60 years), and surgical procedure type. Results are exploratory and are interpreted descriptively without multiplicity adjustment.

10. Handling of Missing Data

Missing data are not anticipated for the primary endpoint, given that intraoperative HRV is recorded continuously throughout the surgical procedure. Should missing or invalid data occur, the following rules apply:

- HRV signal validity: epochs containing artifact are excluded prior to RMSSD computation. Participants must have $\geq 75\%$ valid R-waves throughout the intraoperative recording to be included in the primary analysis. Participants below this threshold are treated as having missing primary outcome data.

- Missing post-test STAI or VAS: participants with missing T3 values for a secondary endpoint are excluded from the analysis of that endpoint only, with missingness reported by group.
- Primary endpoint missingness $\leq 5\%$: complete-case analysis is reported as the primary analysis.
- Primary endpoint missingness $> 5\%$: multiple imputation ($m = 50$) under a missing-at-random (MAR) assumption is used as the primary approach, with complete-case analysis reported as a sensitivity analysis. A tipping-point sensitivity analysis is additionally reported.

11. Handling of Multiplicity

There is a single primary endpoint (intraoperative InRMSSD), tested at $\alpha = 0.05$ (two-sided). No multiplicity adjustment is required for the confirmatory inference.

The two secondary endpoints (postoperative STAI-State and postoperative VAS) are interpreted as supportive, with each tested at the nominal $\alpha = 0.05$ without multiplicity adjustment. Conclusions regarding secondary endpoints are framed accordingly. No formal hierarchical or gatekeeping testing procedure is applied.

12. Interim Analyses and Data Monitoring

No formal interim analyses involving statistical testing of the study hypotheses are planned. No formal stopping rules are prespecified. A Data Monitoring Committee is not established for this low-risk, non-pharmacological behavioral intervention.

13. Safety Considerations

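### The primary analysis lets an interaction test choose between two routes to a positive result and states no success rule for the second, so the 5% two-sided error in Section 11 is not controlled

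*Combined protocol and SAP*

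**What the plan says.** Section 11 states: "There is a single primary endpoint (intraoperative InRMSSD), tested at $\alpha = 0.05$ (two-sided"), and adds: "No multiplicity adjustment is required for the confirmatory inference".

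Section 9.3 fits a model with group, baseline lnRMSSD, their interaction, age and sex. "The homogeneity of regression slopes assumption is evaluated by the significance of the Group \times Baseline lnRMSSD interaction term". It continues: "The analysis path is conditional on this test". The p-value, cut at .05, then selects the primary analysis:

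- **Path A (p ≥ .05).** "If the homogeneity-of-slopes assumption holds, the interaction term is removed and a standard ANCOVA is fitted". The adjusted mean difference is reported with its p-value.
- **Path B (p < .05).** The interaction stays in the model. Four outputs are listed, among them "iii) the J–N region(s) of significance" and the share of the sample inside each region. No critical value, simultaneous limit or overall treatment test is given, and no rule for when the result supports H1.

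Section 7 carries the same switch into the estimand: the population-level summary is the adjusted mean difference under Path A and the regions under Path B. Section 9.4 extends the scheme: "If violated for a secondary endpoint, the J–N procedure is applied analogously to the primary analysis".

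Section 14 lists ANCOVA as prospectively specified in the IRB-approved protocol. It describes the Johnson–Neyman procedure as a response to a slope violation that had been observed.

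**The concern.** One endpoint is not the same as one test. The interaction test gives a 5% chance of entering Path B when nothing is going on. Once there, a region of significance almost always lies inside the data. In the other 95% of trials, the ANCOVA group test gives its own 5% chance. The two chances nearly add, because the interaction and group tests are close to independent.

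Because Section 7 makes the regions the primary summary, Path B cannot be read as a mere diagnostic. At stake is the error rate of the trial's only confirmatory claim. A finding that the ball works in patients with low (or high) baseline lnRMSSD could be presented as the primary result, under a 5% label that the procedure does not earn.

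**Working it through.** **Inputs from the SAP.** Two-sided alpha 0.05 (Sections 8.2 and 11); path cut-off .05 and covariates (Section 9.3); 1:1 allocation (Section 3); 37 per group enrolled and 32 per group evaluable (Section 4).

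**Assumptions.** The documents give no baseline–outcome correlation; 0.5 is used. It hardly matters, because baseline is in both models: runs at 0 and 0.5 gave the same rates. Pointwise limits are assumed for the regions, since Section 9.3 states no other and Section 8.2 sets a nominal .05 throughout.

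**1. The plan's own figures.** For d = 0.71, n per arm = 2 × (1.96 + 0.84)² / 0.71² = 31.1, so 32. Exact power at 32 per arm is 0.798, so the stated 64 reproduces. That calculation is for one two-group comparison at 0.05. A single ANCOVA group test, used whatever the interaction result, also reproduces the 5%: 4.98% in 100,000 simulated null trials with 37 per arm.

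**2. Two-path rule, by arithmetic.** If every significant interaction counts as positive:

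0.05 + 0.95 × 0.05 = 0.0975.

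**3. Two-path rule, by simulation.** Null trials had no group effect and no interaction, with age and sex in the model. Under Path B the effect at baseline x is b1 + b3·x, with standard error √(V11 + 2x·V13 + x²·V33). It is compared with the t critical value on 74 − 6 = 68 degrees of freedom (about 2.00) across the observed range of x. With 37 per arm and 100,000 trials:

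- interaction p < .05: 4.93%
- Path A and ANCOVA p < .05: 4.74%
- Path B with a region inside the observed range: 4.69% (4.69 / 4.93 = 95% of chance interactions)
- total: 4.74 + 4.69 = 9.43% (Monte Carlo standard error 0.09 points)

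**4. Dependence on the missing success rule.** Ranges are over repeat runs; those for the any-region and single-test rows also include 32 per arm and a skewed baseline.

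| Path B counts as positive if | Total false-positive rate |
|---|---|
| any region in the observed range | 9.1–9.9% |
| region covers ≥ 10% of the sample | 8.5–8.8% |
| region covers ≥ 25% | 7.3–7.6% |
| region covers ≥ 50% | 5.0–5.3% |
| effect at mean baseline is significant | 4.8–5.1% |
| (no paths: one ANCOVA test always) | 4.9–5.3% |

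**5. H1 direction only.** Counting a positive ANCOVA or any region favouring the intervention gives 5.3–5.7%, against 2.5% for one two-sided 5% test.

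**6. Correcting the regions alone.** The simultaneous (Potthoff) critical value is √(2 × F(.95; 2, 68)) = about 2.50. Keeping both paths with this limit still gives about 7.0%, because Path A's 4.7% is untouched.

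**7. Is the pre-test needed?** With a true slope difference of 0.6 and zero average effect, plain ANCOVA rejected in 5.1% of trials. With 1:1 allocation, its group coefficient remains a sound test of the average effect.

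**The case against.** The strongest reply is that the SAP never says any region counts as a positive result. It lists outputs, including the share of the sample in each region, and a careful author might claim success only for a large region favouring the intervention. This stands, and it limits the claim. A reader might infer that the plan's false-positive rate simply is 9.5%. The documents do not support that: 9.5% belongs to the most liberal reading, and the table shows how far it falls under stricter ones. H1 is also directional, and about 39% of chance Path B results (1.8 of 4.6 points) showed regions in both directions, which would not plainly support it. But the rules that bring the rate near 5% are absent from the SAP, and that absence is the defect.

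Second, Section 9.3 does not say the regions are pointwise. That is an inference from Section 8.2 and the absence of any stated correction. It is the likely reading, but not a stated one, and simultaneous limits alone would leave about 7%.

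Third, Johnson–Neyman is a recognised follow-up when slopes differ. That is true as a description of moderation. It does not turn regions reached through a pre-test into a 5% test of H1. When slopes truly differ, the regions can reflect real conditional effects; they still do not establish an average benefit.

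A reader might also carry the calculation over to all three endpoints. Section 11 calls the two secondary endpoints supportive, and any joint figure would need their correlation, which is not given. No such figure is offered here.

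**Conclusion.** The point holds in a conditional form. The SAP offers two unguarded routes to a primary result and no Path B success rule, so the two-sided 5% in Section 11 is not controlled. Under the global null the rate runs from about 5% to about 9.5%, depending on a rule the SAP leaves open; in the H1 direction, with any favourable region counted, it is about 5.5% instead of 2.5%. Sample size and baseline skew change this little.

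These are long-run rates for a rule fixed in advance. Section 14 says the Johnson–Neyman path answered an observed violation and lists only ANCOVA as prospectively specified, so the simulations omit a further dependence on the data. A reader might infer that this trial's own result is a false positive. Nothing in the documents shows that; they show only that the stated error rate cannot be relied on.

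**What to change.** - **Section 9.3:** make the group coefficient of the no-interaction ANCOVA the single confirmatory test, fitted whatever the interaction p-value. Its error is about 5%, including when slopes differ and the average effect is zero.
- **Section 7:** make the population-level summary the adjusted mean difference with 95% CI, without condition.
- **Sections 9.4, 9.5 and 15(iii):** remove the dependence on Path A or Path B so that they match.
- **Interaction test and Johnson–Neyman regions:** report as exploratory only, preferably with simultaneous limits (critical value about 2.50). Section 9.6 works without multiplicity adjustment, so this is a preference, to be stated where the regions are reported. It does not replace the first change.
- **Section 11:** its sentence on multiplicity can stay once these changes are made.
- **Section 14:** record that the change came after the slope violation was seen, and that it returns the confirmatory test to the prospectively specified framework.

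The cost is SAP wording and a re-run of models already described. The downside is that Johnson–Neyman regions are no longer confirmatory, so a benefit confined to part of the baseline range could be reported only as a hypothesis.

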3.3 Intervention

All participants receive standard perioperative nursing care under local anesthesia using a mixture of 5 mL of 2% lidocaine, 5 mL of normal saline, and 0.1 mL of epinephrine (1 mg/mL), yielding an approximate final epinephrine concentration of 1:100,000, without tourniquet.

Following completion of all baseline assessments (T1), participants in the IG receive a commercially available soft foam stress ball (6 cm in diameter, moderate resistance) in their non-operative hand. A trained research assistant delivers standardized verbal instructions, asking participants to squeeze the ball rhythmically at a rate of once every three seconds while focusing attention on the ball, with the opportunity to practice before entering the operating room. The intervention commences at the initiation of surgery and continues until completion. Participants in the CG rest the non-operative hand naturally on the arm board without any object.

4. Sample Size Justification

(Prospectively specified in the IRB-approved protocol.)

Sample size was determined a priori using G*Power v3.1.9 ($\alpha = 0.05$ two-tailed; power = 0.80). Because no prior randomized controlled trial had examined the effect of stress ball use on HRV-based outcomes at the time of trial design, an effect size of Cohen's $d = 0.71$, derived from post-procedure pain scores in a randomized controlled trial of stress ball use during unsedated endoscopy (Karatas & Gezginci, 2023), was used as the reference effect size. This study was selected as the closest available proxy given its use of the same intervention in a comparable invasive procedural context.

The calculation indicated that 64 participants (32 per group) would be required to detect the reference effect. Allowing for an anticipated 10% attrition rate, the target enrollment was set at 74 participants (37 per group). The acknowledged limitation that the reference effect size derives from a subjective pain outcome rather than an HRV-specific endpoint is discussed in the limitations section of the primary publication.

5. Analysis Populations

The following analysis populations are defined for this analysis:

Population	Definition
Full Analysis Set / ITT	All randomized participants, analyzed according to the group to which they were randomized regardless of intervention received. The FAS is the primary analysis population for all efficacy endpoints.

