6.1 Primary Endpoint

(Prospectively specified in the ClinicalTrials.gov registration as “Heart Rate Variability”).

Intraoperative HRV, operationalized as the natural log-transformed root mean square of successive differences (lnRMSSD), recorded continuously during the surgical procedure (T2) with the participant in the supine position.

HRV Acquisition and Preprocessing

- Device: portable ECG recorder (Amor HRV Guard, model 8z05; Leadtek Research Inc., Taiwan).
- Sampling rate: 500 Hz.
- Recording position: supine throughout the surgical procedure.
- Validity criterion: a minimum R-wave validity of 75% is required for inclusion in the primary analysis. RMSSD remains valid when up to 36% of beat-to-beat intervals are removed (Sheridan et al., 2020); the 75% threshold provides a conservative margin appropriate to the intraoperative environment.
- Transformation: because raw RMSSD values are typically right-skewed, a natural logarithmic transformation is applied prior to all analyses, in accordance with Laborde et al. (2017). The transformed variable, lnRMSSD, is used in all subsequent analyses.

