9.5 Sensitivity Analyses

- Per-Protocol analysis: the primary analysis (Path A or Path B) is repeated in the PP set.
- Unadjusted analysis: independent-samples t-test (or Mann–Whitney U) on T2 lnRMSSD without baseline or covariate adjustment.
- Covariate-minimal model: Path A or Path B fitted without age and sex, to assess covariate contribution.
- Influence diagnostics: standardized residuals from the primary model are inspected; analyses are repeated excluding observations with $|\text{standardized residual}| > 3$.

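### Under Path B, a significant log-scale interaction cannot separate a benefit confined to low-baseline patients from a similar millisecond gain for everyone, and no Section 9.5 check would show the difference

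*Combined protocol and SAP*

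**What the plan says.** Section 6.1 gives the reason for the log scale: "because raw RMSSD values are typically right-skewed, a natural logarithmic transformation is applied prior to all analyses". It adds: "The transformed variable, lnRMSSD, is used in all subsequent analyses". Section 9.2 repeats the skewness argument, and Section 14 calls the transformation a methodological convention. H1 (Section 2.3) and the estimand variable (Section 7) are also stated on lnRMSSD.

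Section 9.3 chooses the primary path by the significance of the Group × baseline lnRMSSD term. Under Path B, "the conditional treatment effect across the range of baseline lnRMSSD values is examined using the Johnson–Neyman (J–N) procedure". The output is the region or regions of significance, the share of the sample in each, and a plot of conditional effects. Section 7 makes the regions the population-level summary when slopes differ.

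Section 9.5 lists four checks. Three rerun the primary model: in the per-protocol set, without age and sex, or without outlying residuals. The fourth is "Unadjusted analysis: independent-samples t-test (or Mann–Whitney U) on T2 lnRMSSD without baseline or covariate adjustment", which has no baseline term at all. The SAP plans no analysis in ms and no back-transformation, and it does not say that a proportional effect is expected. Section 14 describes the slope violation as observed, so Path B has been reached.

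**The concern.** Whether an effect depends on baseline depends on the scale of the outcome. On lnRMSSD, equal slopes mean the same percentage change for everyone. If the stress ball instead adds about the same number of ms for everyone, the log difference is large at low baseline and small at high baseline, and the slopes differ for that reason alone.

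The SAP argues for the log scale on skewness and convention. That is a sound basis for estimating an average effect. Path B asks more of the scale: it decides whether an average effect is reported and which patients lie inside a region of significance. With Path B reached, those regions are likely to be the main message of the publication. High-baseline patients who gained as many ms as the rest could then be read as not benefiting.

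**Working it through.** **The plan's own figure.** Section 4 uses d = 0.71, two-sided 0.05 and power 0.80. The normal approximation gives 2 × (1.960 + 0.842)² / 0.71² = 31.1, so 32 per group, which matches "64 participants (32 per group) would be required to detect the reference effect". With 10% attrition, 64 / 0.9 = 71.1, so 72. An exact t calculation gives power 0.798 at 32 and 0.811 at 33 per group, and 66 / 0.9 = 73.3 gives the stated 74. The difference is not material here. The simulations use 37 per group.

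**Algebra (no assumptions).** A gain of c ms on an RMSSD of x ms is ln((x + c)/x) on the log scale, which falls as x rises. For c = 8:

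| RMSSD without the ball | Ratio | Log difference |
|---|---|---|
| 15 ms | 23/15 = 1.53 | 0.43 |
| 30 ms | 38/30 = 1.27 | 0.24 |
| 60 ms | 68/60 = 1.13 | 0.13 |

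**How often this triggers Path B.** The gain acts on the T2 value, and the test uses the T1 value, so the result depends on the T1–T2 correlation. The documents give neither that correlation nor any RMSSD mean or SD. Assumptions: log-normal RMSSD, median 25 ms, SD of lnRMSSD 0.4–0.8, 4,000 trials per setting, the Section 9.3 model with interaction, age and sex. The true effect is one ms gain for all, sized to d = 0.71 on lnRMSSD (6.8, 9.9 and 12.8 ms at SD 0.4, 0.6 and 0.8).

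| T1–T2 correlation | Log-scale interaction p < .05 | Same test in ms, HC3 |
|---|---|---|
| 0.3 | 6–9% | 4–5% |
| 0.5 | 9–17% | 5% |
| 0.7 | 16–39% | 5–6% |
| 0.85 | 36–77% | 5–6% |

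In about 85% or more of the log-scale rejections, benefit was significant at the lowest baseline and not at the highest. In those trials a median of 15–35% of the sample lay outside the region. The ms test was not significant in 56–95% of the log-scale rejections.

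**Controls.** Under a constant ratio with the same d (SD 0.6), the log-scale test rejected in about 5% and the ms test in 5–33%, rising with the correlation. With half the effect (median 30 ms, SD 0.5–0.7, correlation 0.4–0.75), a constant ms gain gave 6–19% on the log scale.

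**Check at correlation 0.75.** I reran the simulation with median 30 ms, SD 0.5, 0.6 and 0.7, and 4,000 trials each. Sizing d on the control SD gave 33%, 44% and 53%; sizing it on the pooled SD gave 28%, 36% and 44%. Roughly 35–50% is therefore a fair summary, with a lower edge nearer 28% on pooled sizing. Across the d = 0.71 runs at correlations 0.3, 0.5 and 0.75, the ms interaction estimate had the same sign as the significant log one in 72–99% of Path B trials. Agreement in sign is therefore weak reassurance.

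**The case against.** The strongest reply is that the log scale is the trial's declared question. The endpoint, H1 and the estimand are all on lnRMSSD, the transformation is conventional, and a log-scale interaction answers a log-scale question correctly. This stands. A reader might infer that the log scale is a mistake or that ms is the true scale, but nothing in the documents supports either. The problem is symmetric, as the 5–33% rejection rate in ms under a constant ratio shows. The near-nominal ms rate under a constant ms gain is true by construction.

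Relevance is also uncertain. A uniform ms gain produces only one pattern, a positive effect that shrinks with baseline, and the direction of the observed interaction is not stated. The Section 9.3 plot would show the direction, and a log effect that grows with baseline would argue against this explanation. The plot cannot confirm it, though, because both explanations predict the same falling curve.

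The frequencies rest on outside assumptions. T1 is seated rest (Section 6.3) and T2 is supine during surgery (Section 6.1), so the correlation may be modest and the excess over 5% small. The d of 0.71 was "derived from post-procedure pain scores in a randomized controlled trial of stress ball use during unsedated endoscopy", not from HRV.

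Finally, the SAP does not itself say that patients outside a region gain nothing. That misreading of Johnson–Neyman output can occur on any scale. But the SAP does not guard against it either.

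**Conclusion.** The concern holds in a limited form. Under Path B, the planned analyses cannot distinguish a benefit confined to low-baseline patients from a similar ms gain for all, because the interaction, the regions and every sensitivity check use one scale. The algebra needs no assumption. The frequency does: at d = 0.71, about 6–9% of trials at a T1–T2 correlation of 0.3 and roughly 35–50% at 0.75, with the RMSSD median and SD also assumed.

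Two stronger conclusions are not supported:

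- **That the observed violation is an artefact of scale.** The documents give neither its direction nor its size.
- **That effect modification should be claimed only if significant on both scales, or if the effect changes sign.** Requiring both scales cut power for a genuine log-scale interaction (slope change 0.6) from 74–95% to 51–74%. A sign change is no safeguard: at d = 0.71 with a constant ms gain, the fitted log effect crossed zero within the observed baselines in 73–94% of Path B trials, across two sets of runs.

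This is an inexpensive improvement in reporting and interpretation. It does not challenge the primary endpoint.

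**What to change.** Keep lnRMSSD as the primary scale and make these additions:

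- **Section 9.5.** If Path B is taken, refit the same model with RMSSD in ms and HC3 standard errors, labelled as added after the slope violation was observed. Report the conditional effect with 95% CI at the 10th, 50th and 90th percentiles of baseline, both as a back-transformed ratio from the log model and as a difference in ms.
- **Sections 9.3 and 15.** State that the Johnson–Neyman regions describe the proportional (log-scale) effect and that lying outside a region is not evidence of no benefit. If the ms effect does not vary with baseline in the same direction, word the finding as a difference in percentage effect only. Where the directions agree, show the ms interaction with its CI and do not treat agreement alone as confirmation.
- **Section 14.** List the ms refit among the elements specified after the data were seen.

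The cost is one extra model on data already held and a few lines of text. The downside is a more cautious claim of effect modification.
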